Telemonitoring with hand-held home spirometry has been shown to be a reliable and valuable tool for monitoring health in respiratory illnesses. Russell demonstrated that daily measurement of FVC in IPF patients is more sensitive than hospital-based measures in predicting prognosis and at time points earlier than had been possible with traditional periodic monitoring (16). Respiratory patients benefit from home spirometry use by predicting re-exacerbation (17), allowing earlier tapering of steroids (18), and decreased healthcare costs in both compliant and non-compliant cystic fibrosis patients. (19) Asthma patients reported home use of spirometry was 'not complicated' and the vast majority remained interested in using a home system of monitoring their lung disease. (20)

Combined structured telephone calls with telemonitoring demonstrate further benefit across chronic care conditions including respiratory-related diseases. Celler demonstrated significant drops in healthcare expenditures, reduced admission rates to hospitals, and reductions in hospital stays among patients with COPD, CAD, HTN, DM, and asthma (21). Inglis completed a meta-analysis of 41 randomized clinical trials of heart failure patients and showed that structured telephone calls with non-invasive home monitoring reduced the risk of all-cause mortality and heart failure related hospitalizations as well as improved quality of life, overall disease knowledge, and self-care behavior (22).

We propose that structured telenursing with non-invasive remote monitoring of newly diagnosed IPF patients will, due to improved levels of patient education and understanding, decrease hospitalizations for respiratory illness, decrease visits to emergency centers or urgent care centers, increase compliance with therapies such as medication, oxygen, and rehab, and ultimately increase quality of life. This increased education and oversight of patients by nurses and nurse practitioners trained in the management of patients with Idiopathic Pulmonary Fibrosis will allow for earlier recognition of complications and exacerbations that we hypothesize will ultimately show an impact on mortality.

Hypothesis

Telenursing with or without remote monitoring will reduce the rate of hospitalization, and positively affect other variables, as compared to usual care (control group).

Endpoints

Primary Endpoint

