1. To determine if the total number of hospitalizations related to respiratory event is lower in the interactive arms (Arm 2 and Arm 3) than in the control group (Arm 1).

Secondary Endpoints

1. To recognize, evaluate, and treat respiratory events through telecommunications with or without remote monitoring before the requirement of hospitalization or result of death.
2. To improve compliance in multiple areas noteworthy to IPF patients as measured by various means during clinic appointments to help guide further understanding and education:
 - a. IPF medication compliance – by patient report/diary
 - b. Laboratory follow up – by patient report and collection of laboratory reports
 - c. Attendance in pulmonary rehab or other formal exercise program – by patient report and/or collection of rehabilitation records
 - d. Supplemental oxygen use – by patient report
 - e. Management of comorbidities
 - i. GERD – by patient report of medication use and lifestyle changes
 - ii. OSA – by collection of compliance reports of pap therapy, or notes of such contained in office notes
 - f. Vaccines – by patient report
3. To improve quality of life scores as demonstrated by QOL questionnaires
4. To compare hospitalization parameters of “time to first hospitalization”, length of stay, number of hospitalizations per individual, and outcomes (such as quality of life post-hospitalization), discharge status [alive, deceased], discharged to [home, hospice facility].
5. To improve patient knowledge of lung disease, treatments, and management as demonstrated by self-report
6. To compare measurements obtained by clinic spirometry and home spirometry and clinic pulse oximetry and home oximetry.

Exploratory Endpoints

Exploratory endpoints will be collected to determine if the activities related to telehealth and remote monitoring will positively affect physiology and mortality.

1. To evaluate the difference in forced vital capacity (FVC) from baseline/diagnosis among the groups and as stratified by class
2. To evaluate the difference in walk distance in six minutes from baseline/diagnosis among the groups and as stratified by class

3. To compare findings in annual echocardiography in regards to right ventricular size and function and pulmonary hypertension from baseline/diagnosis among the groups and as stratified by class
4. To evaluate mortality differences among the groups and as stratified by class

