The patient will be asked to measure his pulmonary function at about the same time every day, preferably after completion of the pulse oximetry measurement. Patients will be asked to sit and complete spirometric maneuvers by following the directions and instructions provided by the device and telehealth team. The data will immediately be seen by the patient on his or her smartphone or tablet.

During each healthcare provider-directed appointment, patients will be given specific individualized instruction regarding when to contact their healthcare team should their results begin to decline. Each patient will be instructed to contact the office if their FVC drops by 5% for 3 days in a row (example: from 3.0L to 2.85L). More information about the Spirobank Smart spirometer is located in Appendix 10.

A Flowchart that simplifies the decision-making and assigning of tools is located in Appendix 11.

Patient Selection

Every patient who is diagnosed with IPF by a Vanderbilt physician, who is scheduled for an out-patient visit will be pre-screened to ensure inclusion criteria are met and exclusion criteria are not met.

Inclusion Criteria. The patient must meet all inclusion criteria.

1. Patient must be diagnosed with IPF by a Vanderbilt pulmonologist according to the 2011/2018 ATS Guidelines (3/24).
2. FVC $\geq 40\%$.
3. Willingness to complete Quality of Life and Compliance Questionnaires at 6-month intervals either via an on-line process (RED Cap survey) or paper-based.
4. Willingness to participate in phone calls/video calls with the nurse practitioner or nurse case manager, if assigned to Arm 2 or Arm 3.
5. Willingness to complete and monitor daily physiologic assessments, if assigned to Arm 3.
6. Willingness to share objective data via a provided electronic web-based portal, electronically via email, fax, or regular mail.
7. Willingness to notify, or allow notification, of study involvement with local pulmonary practices.

Exclusion criteria. If the patient meets any of the following exclusion criteria, he or she cannot participate:

1. Diagnosed with any other interstitial lung disease.
2. Listed for lung transplant.
3. Requires supplemental oxygen $> 5\text{L}$ at rest.
4. Experiencing an acute exacerbation of IPF.
5. Recently hospitalized for respiratory event.
6. Not willing to complete questionnaires.
7. Not willing to participate in educational and management phone calls/video calls.

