8. Not willing to complete and share objective data via a provided electronic web-based portal, electronically via email, fax, or regular mail.
9. Not willing to notify, or allow notifications, of study involvement with local pulmonary practices.
10. Any comorbidity or other reason why the investigator believes the patient would not be an acceptable candidate to enter the study.

If the patient meets candidacy during pre-screening, his or her potential participation will be reviewed with the healthcare provider to ensure eligibility on the day of the out-patient visit, preferably after the provider has completed the health history and physical examination. Once confirmed, the study team will consult the patient, advised him or her of the study, and determine if he or she would be willing to participate. Those who do not consent, will be asked their reason why, and these will be recorded (see Appendix 12). Those who agree will sign the consent.

Randomization

The randomization schedule will be generated prior to study initiation using a permuted-block randomization with varying block sizes of 2 to 3 assignments per arm. Patients who sign consent will be randomized by this schema to one of the three arms of the study. The permuted block will be set up in RED Cap and available for the study team to utilize. Randomizations will be structured so that patients will be stratified by degree of illness and then randomized in order to have equal numbers of patients in

each of the severities of illness. The randomization schedule will be uploaded to the RED Cap module so that a study participant's intervention assignment is only revealed after entry of consent documentation. Pre-screening and enrollment activities will begin upon Vanderbilt Human Research Protection Program (IRB) approval.

Confidentiality

All attempts will be made to ensure patient confidentiality.

Patients who agree to participate and sign the consent will be assigned a study identifier known only to the study staff for data entry purposes. The code for study identifiers will be the arm of the study and next sequential two-digit number of enrollment, therefore, a patient who is consented to the study and was sequentially randomized to Arm 2, would have the next sequential two-digit participant number, so that the third participant into Arm 2 would be assigned a study identifier of 2-03.

Data Collection

Data will be collected in RED Cap.

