300	0.25	0.19	0.15	0.77	0.58	0.84	0.38	0.90

At least 80% power for the joint treatment effect and the A3 vs A1 effect was achieved when the event rate was .25, .19, and .15 for the three arms, respectively. The power for the comparison between A2 and A1 was 0.38, which was the highest of all the situations considered.

Proposed statistical analysis plan for the primary endpoint

The primary endpoint will be an ordinal variable that is a composite of hospitalizations and death within one year of diagnosis. The categories of the ordinal variable will be: 0 hospitalizations & no death, 1 hospitalization & no death, ..., K hospitalizations & no death, and then death as the final category. This will order the patients from best to worst outcomes in a way that incorporates the possibility of death.

The primary endpoint will be analyzed with a cumulative probability ordinal regression model which includes treatment assignment indicators and relevant covariates, such as age, gender, race, and other measures of baseline disease severity like **time-since-diagnosis**. Continuous variables, such as age, will be included in the model with restricted cubic splines in order to allow for the possibility of a non-linear association with the outcome. Model diagnostics, such as DFBETAs, will be generated to identify overly influential observations.

Once the regression model diagnostics indicate the model is reasonably fit, the treatment effect will be tested with Wald statistics at the $\alpha=0.05$ type I error level. The first effect to be tested is the joint treatment effect. If the joint effect is significant, then A3 vs A1 and A2 vs A1 will be tested. If the joint effect is not significant, no additional pairwise comparisons will be tested. The sequential test strategy ensures that the type I error rate is preserved.

As a sensitivity analysis, we will analyze hospitalization rates (not the composite hospitalization and death) with a model similar to the one described above.

Every effort will be made to collect covariate information; however, if missing data exists in the analysis dataset, we will adjust the analysis described above and implement multiple imputation with predictive mean matching. At least 30 imputations will be generated.

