- B. No, I do not take my medication for reflux / GERD daily, but take it most days of the week. (2)

- C. No, I only take my reflux / GERD medication less than half the days in a week. (1)
- D. No, I only take my reflux / GERD medication when I need it. (1)
- E. No, I do not take my reflux / GERD medication. (0)
- F. This is not applicable to me because I am currently not prescribed reflux / GERD medication. (n/a)

Do you wear your cpap or bipap mask every time you sleep?

- A. Yes, I wear my cpap or bipap every night. (3)
- B. No, I wear my cpap or bipap most days a week (at least 4 days a week). (2)
- C. No, I wear my cpap or bipap less than 4 days a week. (1)
- D. No, I do not wear my cpap or bipap. (0)
- E. This is not applicable to me because I do not have sleep apnea that requires treatment with cpap or bipap. (n/a)

Knowledge section

I understand my lung disease.

- A. Completely agree
- B. Mostly agree
- C. Somewhat agree
- D. Do not agree

I understand how my IPF medication has been shown to help me.

- A. Completely agree
- B. Mostly agree
- C. Somewhat agree
- D. Do not agree

I understand the side effects associated with my IPF medications.

- A. Completely agree
- B. Mostly agree
- C. Somewhat agree
- D. Do not agree

I understand the importance of regular exercise.

- A. Completely agree
- B. Mostly agree
- C. Somewhat agree
- D. Do not agree

I understand why I need (or may need) to wear oxygen.

- A. Completely agree
- B. Mostly agree

- C. Somewhat agree
- D. Do not agree

I know when to call my IPF healthcare provider.

- A. Completely agree
- B. Mostly agree
- C. Somewhat agree
- D. Do not agree

APPENDIX 7: TELENURSING OUTLINE AND SCRIPTS FOR EDUCATIONAL, MANAGEMENT, and RECOGNIZED RESPIRATORY EVENT TELEPHONE CALLS

Introductory Phone Call – with the nurse practitioner and within the first week of the initial visit

Purpose 1: IF NOT CONSENTED TO THE STUDY IN THE CLINIC – the NP will discuss this study with the patient during the usual care appointment follow-up phone call. If the patient verbally agrees, a consent will be sent to the patient for signature and randomization will occur.

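### The primary endpoint's one-year window starts at diagnosis rather than at randomization; the loss is probably small, but correcting it is free

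*Combined protocol and SAP*

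**What the plan says.** The section on the proposed analysis of the primary endpoint describes an ordinal outcome that is a "composite of hospitalizations and death within one year of diagnosis". The model for it adjusts for "relevant covariates, such as age, gender, race, and other measures of baseline disease severity like" time-since-diagnosis.

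Assignment comes later than diagnosis. Under Randomization, the "intervention assignment is only revealed after entry of consent documentation". Appendix 7 also allows for patients who did not consent in clinic: the study is raised in a call "with the nurse practitioner and within the first week of the initial visit", and a consent form is then sent out for signature. No deadline for its return is given.

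Under Patient Selection, "Every patient who is diagnosed with IPF by a Vanderbilt physician, who is scheduled for an out-patient visit will be pre-screened". None of the inclusion or exclusion criteria sets a maximum time since diagnosis. One exclusion bears on early events, "Recently hospitalized for respiratory event", but the word for recent is not defined.

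Other text points to prompt enrolment. The background proposes "structured telenursing with non-invasive remote monitoring of newly diagnosed IPF patients", Appendix 12 describes the screening log in terms of newly diagnosed patients, and the first exploratory endpoint reads "To evaluate the difference in forced vital capacity (FVC) from baseline/diagnosis among the groups", which treats baseline and diagnosis as one time point. Study Design schedules the first questionnaires at diagnosis.

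**The concern.** Assignment cannot change anything that happens before randomization. With the clock starting at diagnosis, any gap before randomization lies inside the outcome window, and the plan does not say how hospitalizations in that gap are handled. Death cannot occur in the gap, because a patient must be alive to be randomized.

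There are two readings. If earlier hospitalizations count, every arm carries the same untreated events and the treatment contrast shrinks. If they do not, the relative risk is roughly preserved, but the treated window and the number of events fall, and by different amounts in different patients. A time-since-diagnosis covariate cannot recover treated follow-up that lies outside the window. Its presence in the model also shows that the plan expects the gap to vary.

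What is at stake is power and a conservative effect estimate. Events before randomization are balanced between arms in expectation, so there is no false-positive problem.

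**Working it through.** **Inputs.** Planned size is 50 per arm (Study Design). The Arm 1 one-year risk is 0.25, and the most favourable scenario in the power table has a relative risk of 0.58 for Arm 3, so the Arm 3 risk is 0.58 × 0.25 = 0.145 (shown rounded as 0.15). The test is the Wald test from a logistic model at 0.05, taken as two-sided. The gap t between diagnosis and randomization is an assumption, because the documents give none.

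**Reproducing the plan's figures.** Enumerating both binomials exactly, with the Wald test of the log odds ratio and zero cells treated as non-significant, gives Arm 3 versus Arm 1 power of 0.238 at 50 per arm and 0.902 at 300 per arm. The protocol table has 0.23 and 0.90.

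**Model for the gap.** With a constant hazard per month:

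- λ₁ = −ln(1 − 0.25)/12 = 0.02397
- λ₃ = −ln(1 − 0.145)/12 = 0.01305

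For arm k and gap t in months (one week = 12/52.18 = 0.230):

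- earlier events counted: risk = 1 − exp{−[λ₁t + λₖ(12 − t)]}
- earlier events counted at half the control hazard, as an allowance for the recent-hospitalization exclusion: replace λ₁t by 0.5λ₁t
- earlier events not counted: risk = 1 − exp{−λₖ(12 − t)}

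**Worked case, one month, events counted.** Arm 3 risk = 1 − exp{−[0.02397 × 1 + 0.01305 × 11]} = 1 − exp(−0.1676) = 0.154. Arm 1 stays at 0.25. The relative risk is 0.154/0.25 = 0.62, and power is 0.201.

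**Arm 3 versus Arm 1 at 50 per arm:**

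| Gap | Counted: RR, power | Half hazard: RR, power | Not counted: RR, power (Arm 1 risk) |
|---|---|---|---|
| None | 0.58, 0.238 | 0.58, 0.238 | 0.58, 0.238 (25%) |
| 1 week | 0.59, 0.229 | 0.58, 0.232 | 0.58, 0.234 (25%) |
| 2 weeks | 0.60, 0.221 | – | – |
| 1 month | 0.62, 0.201 | 0.60, 0.211 | 0.58, 0.221 (23%) |
| 3 months (hypothetical) | 0.69, 0.142 | – | 0.57, 0.185 (19%) |
| 6 months (hypothetical) | 0.80, 0.083 | – | 0.56, 0.099 (13%) |

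At 12 months or more, no post-randomization outcome remains in the window.

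**Hypothetical mix.** With 80% of patients at one week and 20% at six months, events counted, the Arm 3 risk is 0.8 × 0.1471 + 0.2 × 0.1992 = 0.1576. The relative risk is 0.1576/0.25 = 0.63, and power is 0.189.

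**The case against.** The best defence is that the wording is loose, not that the estimand is wrong. Study Design lets patients take part even if they never return to the centre after diagnosis, which makes most sense if enrolment happens at or just after the diagnosing visit. Eligibility is to be confirmed on the day of the clinic visit, and the late-consent call falls within a week of it. At one week the power loss is 0.238 − 0.229 = 0.009 if earlier events count and 0.238 − 0.234 = 0.004 if they do not. The protocol's simulation used 4000 replicates, so its own Monte Carlo standard error near 0.23 is √(0.23 × 0.77/4000) = 0.007. A one-week gap is therefore within about the noise of the published table.

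The plan also tests the joint effect first. Simulated with an Arm 2 risk of 0.77 × 0.25 = 0.1925 and earlier events counted, the power to pass the joint test and then find Arm 3 versus Arm 1 significant at 50 per arm is about 0.145 with no gap, 0.140 at one week and 0.12 at one month. The pairwise figures above thus overstate absolute power, although the loss has a similar pattern.

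These points stand as to size, and the three- and six-month rows are not estimates for this trial. They do not remove the problem. Descriptions of the intended population are not eligibility rules, no passage moves the window to randomization, and time-since-diagnosis would be a pointless covariate if the gap were always near zero.

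**Conclusion.** The concern holds, as a free improvement. The stated window can include untreated time and can give patients unequal treated follow-up, with no rule for hospitalizations before randomization. If enrolment is prompt, the cost is about one percentage point of power or less for Arm 3 versus Arm 1. At one month it is between 0.238 − 0.221 ≈ 2 and 0.238 − 0.201 ≈ 4 points. It is larger only for patients enrolled months after diagnosis, whom the criteria permit.

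The figures rest on assumed gaps, a constant hazard and a binary outcome. Those for earlier events counted in full are upper-end illustrations: the planned outcome is ordinal, its death category cannot be reached before randomization, and the exclusion for recent hospitalization removes some early events. Confidence is medium because the actual gap is unknown.

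**What to change.** Define the primary endpoint as hospitalizations and death within 365 days after randomization, counting only post-randomization events, for every randomized patient. Use the same origin for time to first hospitalization and for mortality. Keep time-since-diagnosis as a baseline covariate, and report the days from diagnosis to randomization by arm.

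The cost is a few words in the analysis plan and one descriptive table. Patients are already asked to take part for at least a year (Study Design), and diagnosis, admission and discharge dates are already recorded (Data Collection), so no extra patients, visits or data are needed. If enrolment proves always to be prompt, nothing is lost by the change.

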5. To evaluate patient management at ILD Center compared to outlying community centers among the groups and as stratified by class.
6. To evaluate a standardized protocol that includes a structured educational curriculum followed by a regularly timed disease-focused phone calls with protocolized interventions when disease progression is recognized.

Study Design

This is a single-center prospective randomized study to compare outcomes on hospitalization, healthcare compliance, and quality of life of telenursing with or without remote monitoring as compared to usual care. All patients diagnosed with IPF at the Vanderbilt Medical Center outpatient Pulmonary Clinic, who meet inclusion and exclusion criteria, will be asked to participate. Patients who agree to participate and sign consent will be randomized into one of three treatment arms: usual care (the control group), usual care with telenursing, usual care with telenursing and remote monitoring. Patients will be asked to participate in the study for at least one year. We expect to enroll 150 patients, or 50 patients into each arm.

Usual care (Arm 1) – Patients will continue to receive education in the clinic and telephonically about their lung disease, medications, and oxygen use. At the point of diagnosis, patients will be given our current educational materials to take home and review, as well as our contact information. Patients will continue to attend face-to-face visits in the out-patient setting. The frequency of visits will be based on the discretion of the provider. During these visits, the patient will continue to receive individualized standard of care, which may include some or all of the following: a face-to-face visit with a healthcare provider, vital signs, with pulse oximetry at rest, weight measurement, pulmonary function testing, a six-minute walk, and laboratory testing. Other testing, such as echocardiography or chest radiography, may be required based on need. If patients do not return to Vanderbilt Medical Center beyond the point of diagnosis, they will still be allowed to participate. The usual care of local healthcare providers will be collected.

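### The SAP has no rule for an incompletely observed year in the primary analysis, and its hospitalization-only sensitivity analysis can rank an early death as the best outcome

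*Combined protocol and SAP*

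**What the plan says.** The section on the proposed analysis of the primary endpoint defines the outcome: "The primary endpoint will be an ordinal variable that is a composite of hospitalizations and death within one year of diagnosis". The categories start at "0 hospitalizations & no death" and end with "K hospitalizations & no death, and then death as the final category". The analysis is a "cumulative probability ordinal regression model which includes treatment assignment indicators and relevant covariates". It mentions no offset, censoring rule or minimum follow-up, and no category for patients who withdraw, are lost or are transplanted.

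Missing data get one paragraph: "Every effort will be made to collect covariate information; however, if missing data exists in the analysis dataset", the analysis will be adjusted to "implement multiple imputation with predictive mean matching. At least 30 imputations will be generated". Whether the outcome is among the imputed variables is not stated.

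For the sensitivity analysis, "we will analyze hospitalization rates (not the composite hospitalization and death) with a model similar to the one described above". The text does not say how deaths enter it or what a rate is.

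Three other parts bear on the point:

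- Study Design, usual care arm: "If patients do not return to Vanderbilt Medical Center beyond the point of diagnosis, they will still be allowed to participate". The next sentence provides for collecting the care given by local providers.
- Study Design schedules questionnaires in every arm at diagnosis, 3 months, 6 months and then every 6 months. Arms 2 and 3 add nurse calls, and Arm 3 adds daily home measurements.
- Data Collection lists admission and discharge dates and a health status (alive, dead or transplanted). It does not name a date of last contact.

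**The concern.** A count of admissions seen so far is always a number. Unless a rule says otherwise, a patient last seen in month 2 with no admission can enter the dataset as a zero, the best category, with nothing to trigger imputation. A patient with earlier admissions keeps that count, so the score is too favourable rather than always good.

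This biases the comparison if loss differs by arm, and differential loss is plausible here. Calls in Arms 2 and 3 may keep patients in contact, while daily measurements in Arm 3 may drive some to withdraw, so the bias could run either way. Loss related to prognosis can also distort a true effect.

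The sensitivity analysis has a more direct form of the problem. Once death is removed as a category and nothing accounts for time at risk, dying early shortens the time in which an admission can occur. An arm with more deaths then looks better on hospitalization.

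**Working it through.** **Plan's own figures.** The power section uses a one-year risk of 25% in Arm 1 and, for its 80% power statement, relative risks of 0.77 and 0.58 (risks 0.1925 and 0.145) at 300 per arm. A three-arm logistic simulation with Wald tests (40,000 replicates) gives:

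| Test | Stated | Recomputed |
|---|---|---|
| Joint | 0.84 | 0.833 |
| Arm 2 vs Arm 1 | 0.38 | 0.392 |
| Arm 3 vs Arm 1 | 0.90 | 0.900 |

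The figures reproduce with every patient observed for the full year. The documents give no loss or mortality rate for the trial and no inflation of the sample size, so those rates are assumptions below.

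**Primary analysis, if observed counts are used unadjusted.** Assume a constant hospitalization hazard and loss times uniform over the year, and simplify the outcome to any admission.

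1. Hazard: h = -ln(1 - 0.25) = 0.2877.
2. Risk seen in patients who are lost: 1 - 0.25/0.2877 = 0.131.
3. 5% loss: 0.05 x 0.131 + 0.95 x 0.25 = 0.244.
4. 20% loss: 0.20 x 0.131 + 0.80 x 0.25 = 0.226.
5. Apparent relative risk with no true effect: 0.927, about 0.93.

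Other cases on the same formula:

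- No true effect, 10% vs 30% loss: RR 0.90. With 30% vs 10%: RR 1.11.
- True RR 0.58, 30% loss in Arm 1 and 10% in Arm 3. The hazard in Arm 3 is -ln(0.855) = 0.1567, and the risk seen in those lost is 1 - 0.145/0.1567 = 0.074 (unrounded). Arm 1 shows 0.3 x 0.131 + 0.7 x 0.25 = 0.214, Arm 3 shows 0.1 x 0.074 + 0.9 x 0.145 = 0.138, and the RR is 0.64.
- Equal loss of 0/10/20/30% with the same true risks: RR stays near 0.58, and Arm 3 vs Arm 1 power at 300 per arm falls from 0.90 to 0.88, 0.86 and 0.84.

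**Ordinal check.** Poisson admissions, an assumed death hazard of 0.11 per year, death ranked worst, 3,000 replicates, no true effect, and a Kruskal-Wallis test standing in for the joint ordinal test:

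| Loss in Arms 1/2/3 | Joint type I error, 50 per arm | 300 per arm |
|---|---|---|
| none | 5.5% | 4.7% |
| 15/15/15% | 5.1% | 5.5% |
| 5/15/25% | 5.6% | 10.3% |

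In the last row the apparent Arm 3 to Arm 1 odds ratio for any admission or death is about 0.86. If patients who are lost carry twice the hazards, 20% loss shows 32.5% with a bad outcome where the truth is 37.3%.

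**Sensitivity analysis, followed as written.** Take h = 0.2877 in both arms and one-year mortality of 10% vs 20%, so the death hazards are m = -ln(0.9) = 0.1054 and -ln(0.8) = 0.2231. The chance of an admission before death within the year is h/(h + m) x [1 - exp(-(h + m))].

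- 10% mortality: 0.2877/0.3930 x (1 - 0.75 x 0.9) = 0.732 x 0.325 = 0.238.
- 20% mortality: 0.2877/0.5108 x (1 - 0.75 x 0.8) = 0.563 x 0.400 = 0.225.
- Ratio: 0.225/0.238 = 0.95, favouring the arm with more deaths.

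With person-time the artefact disappears under these assumptions. Mean time at risk is 0.1/0.1054 = 0.949 and 0.2/0.2231 = 0.896 years. Mean admissions are 0.273 and 0.258, and dividing by time gives 0.288 in both arms, a rate ratio of 1.

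**The case against.** The strongest reply is that the plan is silent here and makes no wrong rule. The endpoint is defined over a year, so for a patient lost in month 2 it is undetermined. The imputation condition refers to missing data in the analysis dataset generally, even though the sentence opens with covariates. A reader might infer that the SAP scores dropouts as zero; no sentence says so. That stands, and the point on the primary analysis is therefore conditional.

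A reader might also infer that Arm 1 has no scheduled study contact. It has: the questionnaires apply to all arms, and care from local providers is to be collected for patients who do not return. Leaving the center is not the same as leaving observation, and the calculations above assume that nothing is captured after loss. The difference in contact comes only from the calls in Arms 2 and 3 and the daily measurements in Arm 3.

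The size can be challenged too. The loss rates are assumed, and the RR examples use a binary outcome. An RR of 0.93 matches the smallest Arm 2 effect in the power table, where stated power at 50 per arm is only 0.05. A reader might infer a materially inflated type I error. At the planned 50 per arm the simulated 5.6% is not distinguishable from nominal, and equal non-informative loss mainly costs power.

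Finally, an observed death is already the worst category in the primary analysis, so the early-death problem belongs to the sensitivity analysis alone. There, rates might mean events per person-time. That reading would remove the problem, but the text does not state it, and the ordinal model to which it refers has no time term.

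**Conclusion.** The point holds as a gap in the primary analysis and as a more definite flaw in the sensitivity analysis.

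- **Primary:** the SAP does not say whether a partly observed year is a missing outcome. If it is not treated as missing, the estimate is biased under differential loss: RR 0.93 for 5% vs 20% loss with no true effect, and 0.64 in place of 0.58 for 30% vs 10%. These figures rest on assumed loss rates, a constant hazard, uniform loss times and no capture of events after loss. At 50 per arm the consequence is a biased estimate, with no demonstrable inflation of type I error.
- **Sensitivity:** unless rates means per person-time, an early death without admission falls in the best category. Under assumed mortality of 10% vs 20% the distortion is about 5% on the RR scale, in favour of the arm with more deaths.

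Both should be settled before any data are seen by arm, because a rule chosen afterwards could depend on the result.

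**What to change.** 1. **Sensitivity analysis.** Analyse hospitalizations with a negative binomial model (or Poisson with robust errors), with log observed follow-up time as offset. Follow-up ends at death, transplant, last contact or one year, whichever comes first. State where the clock starts, since the endpoint window is counted from diagnosis. Report the result beside the death-inclusive primary analysis, because the offset treats death simply as the end of exposure.
2. **Primary analysis.** For patients alive but not observed to one year, set the ordinal category to missing. Include it in the planned 30 or more imputations, using arm, randomization stratum, follow-up time and baseline severity. Allow no imputed category below the count already observed. Predictive mean matching does not guarantee this by itself, so the donor pool must be restricted. Say whether transplant ends observation.
3. **Data.** Record a date of last contact for every patient. Admission and discharge dates are already collected.

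A worst-case check on unexplained losses is optional; if added, it must name the ordinal category assigned.

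The cost is SAP wording, one extra date field, modest extra programming and slightly wider intervals.
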